3.4 Rationale for choice of comparator

A placebo will be used as a comparator in this study to ensure the effects of LJN452 are related to the study drug. Recently, the FXR agonist obeticholic acid (Ocaliva™, Intercept Pharmaceuticals) was approved for those with PBC non-responsive to or intolerant of UDCA. However, obeticholic acid is not universally utilized for treatment of PBC. Furthermore, PBC patients with severe itch were excluded from Phase 3 POISE study ([Nevens et al 2016](#)). In order to allow those with severe itch to be enrolled into the study placebo will be used as a comparator.

[Redacted block at the bottom of the page]

3.5 Purpose and timing of interim analyses/design adaptations

The first interim analysis will be performed when at least 12 patients in Cohort 1 have completed 4 weeks of dosing at 0.03 mg and Day 28 post dose assessments. The purpose of this interim analysis is to assess patient safety, to evaluate the assumption on intra-subject variability of GGT, which was used for sample size calculations, and to select a dose for the next cohort. An ANCOVA model will be fitted to estimate the change from baseline in GGT and its variability, and an unblinded sample size re-estimation conducted. The results may be used to adjust the size of the next cohort.

Doses in subsequent cohorts of Part 1 will be decided based on accumulated information collected from all previous cohorts including safety, PK and PD data.

Additional interim analyses will be performed when at least 12 patients in subsequent cohorts of Part 1 have completed 4 weeks of dosing and Day 28 assessments. Placebo data from all cohorts will be pooled in the ANCOVA model to evaluate the treatment difference between each dose level of LJN452 versus placebo. No multiplicity adjustment will be made due to the exploratory nature of the study.

Results from Part 1 will be used to select the doses for Part 2, which may be initiated prior to the completion of Part 1. Part 2 will not be initiated if the estimated change from baseline in GGT at Day 28 is smaller than 20% at the highest dose level of LJN452 in Part 1.

Unblinded interim analysis results from Part 1 will be reviewed by an internal Novartis Interim Analysis Team which may include some CTT members. The Interim Analysis Team may communicate interim results to relevant Novartis teams for information, consulting and/or decision purposes.

In Part 2 of the study, an interim analysis is planned when approximately 40 patients have completed their Week 8 visit. The purpose of this interim analysis is to review the sample size (calculated based on GGT and ALP changes) to assess if it is also adequate to provide precise enough treatment difference estimates in itch parameters, a key tolerability endpoint.

This study will utilize a staggered lock of the clinical database, so that the data can be locked after completion of Part 1, or a set of Cohorts in Part 1.

Once a Cohort's data has been locked, treatment codes for the relevant cohort(s) will be released and made available for data analysis.

The results from the locked Part 1 interim analysis can be communicated beyond Novartis to groups including, but not limited to individuals treating the study's subjects, Health Authorities and reported on clinical registries.

Additional interim analyses [REDACTED] may be conducted to support decision making concerning the current clinical study, the sponsor's clinical development projects in general or in case of any safety concerns. No dose escalation is planned in Part 2.

Additional information is presented in [Section 11.8](#).

3.6 Risks and benefits

There is no benefit expected for subjects participating in this short-term study.

Preliminary data from study CLJN452X2101 have demonstrated isolated increases in transaminases ALT and AST [REDACTED]. These changes normalized spontaneously have not been observed at the proposed starting dose.

The risk to subjects in this trial will be minimized by adherence to the eligibility criteria, close clinical monitoring, and stopping rules.

A maximum of 500 mL of blood is planned to be collected over a period of 16 weeks, from subjects as part of the study (Part 1 sample volume will be approximately 490 mL and Part 2 will be approximately 450 mL). Additional samples for monitoring of any safety findings may be required, and would be in addition to this volume. This is not considered to be a risk for this population.

There may be unknown risks of LJN452 which may be serious and unforeseen.

4 Population

The study population will be comprised of patients with PBC.

In Part 1, a total of approximately 15 patients will be enrolled in each cohort of the study and randomized.

In Part 2, a total of approximately 88 patients will be enrolled and randomized. Final sample size for Part 2 will be informed by the interim analysis.

The investigator must ensure that all subjects being considered for the study meet the following eligibility criteria. No additional criteria should be applied by the investigator, in order that the study population will be representative of all eligible subjects.

Subject selection is to be established by checking through all eligibility criteria at screening and baseline (for Part 1). A relevant record (e.g., checklist) of the eligibility criteria must be stored with the source documentation at the study site.

Deviation from **any** entry criterion excludes a subject from enrollment into the study.

In Part 1 replacement subjects may be enrolled to replace subjects who discontinue the study for reasons other than safety.

4.1 Inclusion criteria for Parts 1 and 2

Patients eligible for inclusion in this study have to fulfill all of the following criteria:

1. Written informed consent must be obtained before any assessment is performed.
2. Age \geq 18 years
3. Diagnosis of PBC as demonstrated by the presence of at least 2 of the following 3 diagnostic criteria:
 - History of Alkaline Phosphatase elevated above upper limit of normal for at least 6 months

- Positive antimitochondrial antibodies (AMA) titer or if AMA negative or in low titer (<1:80) PBC specific antibodies (anti-GP210 and/or anti-SP100 and/or antibodies against the major M2 components (PDC-E2, 2-oxo-glutaric acid dehydrogenase complex))
- Previous liver biopsy findings consistent with PBC

4. At least 1 of the following markers of disease severity:

- ALP $\geq 1.67 \times$ upper limit of normal (ULN)
- Total bilirubin $>$ ULN but $< 1.5 \times$ ULN

In addition, patients must meet the following biochemical criteria at enrollment

- ALT or AST $\leq 5 \times$ ULN
- Total bilirubin $\leq 1.5 \times$ ULN
- INR \leq ULN

5. Subjects must weigh at least 40 kg to participate in the study, and must have a body mass index (BMI) within the range of 18 - 40 kg/m². BMI = Body weight (kg) / [Height(m)]².

6. Able to communicate well with the investigator, to understand and comply with the requirements of the study.

4.1.1 Additional Inclusion Criteria for Part 1

All patients enrolled in Part 1 must meet the following criteria:

1. Taking UDCA for at least 12 months, or for at least 6 months and has reached maximal response to UDCA with a plateau in alkaline phosphatase, (with no changes in dose for ≥ 3 months) prior to Day 1.

4.1.2 Additional Inclusion Criteria for Part 2

All patients enrolled in Part 2 must meet the following criteria:

1. Patients not currently taking UDCA and who have not taken UDCA for ≥ 3 months prior to Day 1 (for example UDCA naïve patients, patients who were unable to tolerate UDCA or had stopped taking due to lack of efficacy) OR Patients taking UDCA for at least 12 months, or for at least 6 months and has reached maximal response to UDCA with a plateau in alkaline phosphatase, (with no changes in dose for ≥ 3 months) prior to Day 1

4.2 Exclusion criteria for Parts 1 and 2

Patients fulfilling any of the following criteria are not eligible for inclusion in this study. No additional exclusions may be applied by the investigator, in order to ensure that the study population will be representative of all eligible patients.

1. Presence of other concomitant liver diseases including:
 - Active Hepatitis B or C virus (HCV, HBV) infection
 - Primary sclerosing cholangitis (PSC)
 - Alcoholic liver disease
 - Definite autoimmune hepatitis
 - Nonalcoholic steatohepatitis (NASH)

- Gilbert's Syndrome

2. Women of child-bearing potential, defined as all women physiologically capable of becoming pregnant, unless they are using highly effective methods of contraception for 30 days before randomization, and will continue to use it during dosing and for 30 days following the end of treatment. Highly effective contraception methods include:

- Total abstinence (when this is in line with the preferred and usual lifestyle of the subject). Periodic abstinence (e.g., calendar, ovulation, symptothermal, post-ovulation methods) and withdrawal are not acceptable methods of contraception
- Female sterilization (have had surgical bilateral oophorectomy with or without hysterectomy) or tubal ligation at least six weeks before taking study treatment. In case of oophorectomy alone, only when the reproductive status of the woman has been confirmed by follow up hormone level assessment
- Male sterilization (at least 6 m prior to screening). For female subjects on the study, the vasectomized male partner should be the sole partner for that subject
- Use of oral (estrogen and progesterone), injected or implanted combined hormonal methods of contraception or placement of an intrauterine device (IUD) or intrauterine system (IUS), or other forms of hormonal contraception that have comparable efficacy (failure rate <1%), for example hormone vaginal ring or transdermal hormone contraception

In case of use of oral contraception women should have been stable on the same pill for a minimum of 3 months before taking study treatment and should complete at least one full cycle after completing dosing.

3. Cirrhosis with complications, including history or presence of:

- Variceal bleed
- Uncontrolled ascites
- Encephalopathy
- Spontaneous bacterial peritonitis

4. Significant hepatic impairment as defined by Child-Pugh classification of B or C, history of liver transplantation, current placement on a liver transplant list or current Model for End Stage Liver Disease (MELD) score ≥ 15 .

5. History of medical conditions other than PBC that may cause increases in ALP (e.g., Paget's disease).

6. History of malignancy of any organ system (other than localized basal cell carcinoma of the skin or treated cervical intraepithelial neoplasia), treated or untreated, within the past 5 years, regardless of whether there is evidence of local recurrence or metastases.

8. History of non-adherence to medical regimens, or patients who are considered to be unable to reliably comply with the requirements of the study.

9. Donation or loss of 400 mL or more of blood within eight (8) weeks prior to initial dosing, or longer if required by local regulation.
10. Use of other investigational drugs or immunosuppressive drugs at the time of enrollment, or within 5 half-lives/30 days of randomization, whichever is longer; (or longer if required by local regulations). Use of high dose oral steroids to treat co-morbid conditions (e.g. airways disease) will be allowed but must be properly documented as such in concomitant medications.
11. Pregnant or nursing (lactating) women, where pregnancy is defined as the state of a female after conception and until the termination of gestation, confirmed by a positive hCG laboratory test.
12. History of drug or alcohol abuse within the 12 months prior to dosing.
13. Significant illness which has not resolved within two (2) weeks prior to initial dosing.
14. Acute or chronic renal disease with a screening serum creatinine > ULN.
15. Elevated liver function tests at screening defined as follows:
 - potential Hy's Law case (defined as ALT or AST > 3 × ULN and TBL > 2 × ULN without notable increase in ALP to > 2 × ULN) or
 - ALT or AST > 3 × ULN combined with INR > 1.5.
 - Total bilirubin > ULN combined with albumin outside of the normal range.
16. Currently taking obeticholic acid or have taken obeticholic acid within 30 days of Randomization.
17. Participation in CLJN452X2201 and received study medication within three months of Randomization (or longer if required by local regulations).
18. History of immunodeficiency diseases, including a positive HIV (ELISA and Western blot) test result.

No additional exclusions may be applied by the investigator, in order to ensure that the study population will be representative of all eligible patients.

5 Restrictions for Study Subjects

During recruitment, screening/informed consent review, and baseline visit, the subjects must be informed and reminded of the following restrictions:

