7.1 Discontinuation of study treatment

Discontinuation of study treatment for a subject occurs when study treatment is stopped earlier than the protocol planned duration. Discontinuation of study treatment can be decided by either the subject or the investigator.

Study treatment **must** be discontinued under the following circumstances:

- Subject decision - subjects may choose to discontinue study treatment for any reason at any time.
- The investigator believes that continuation would negatively impact the safety of the subject or the risk/benefit ratio of trial participation.

- Pregnancy.
- Hypersensitivity reaction to LJN452.
- Hepatic decompensation event such as variceal bleed, uncontrolled ascites, encephalopathy, spontaneous bacterial peritonitis.
- A Liver or Renal event indicating discontinuation as defined in [Table 15-1](#) - Follow up requirements for Liver events or [Table 15-2](#) - Follow up requirements for renal events
- An AE with a CTCAE rating of Grade 3 that are suspected to be related to study drug (apart from pruritus, liver or renal parameters, see [Table 15-1](#), [Table 15-2](#) and [Table 16-1](#) for required actions).
- An AE with a CTCAE rating of Grade 4 or higher, regardless of attribution to study drug
- Emergence of the following adverse events: Diarrhea, nausea, vomiting, recurrent positive fecal occult blood or other GI symptoms that are deemed to be intolerable.

The appropriate personnel from the study site and Novartis will assess whether study treatment should be discontinued for any subject whose treatment code has been broken inadvertently for any reason.

If discontinuation of study treatment occurs, the investigator must determine the primary reason for the subject's premature discontinuation of study treatment and record this information on the Dosage Administration CRF.

After study treatment discontinuation, at a minimum, in abbreviated visits, the following data should be collected at clinic visits or via telephone/email contact:

- new / concomitant treatments
- adverse events/Serious Adverse Events

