^cResolution is defined as an outcome of one of the following: (1) return to baseline values, (2) stable values at three subsequent monitoring visits at least 2 weeks apart, (3) remain at elevated level after a maximum of 6 months, (4) liver transplantation, and (5) death.

Elevation confirmed or persisting, i.e. remain > 90% of the original elevated level

Decreasing elevation, i.e. decrease to ≤ 90 % of the original elevated level.

Table 15-2 Renal events: definition and follow up requirements

Renal Event	Actions
Serum creatinine $\geq 2 \times$ BL or ≥ 1.5 mg/dL	
1. Hold study medication
 
2. Confirm increase after 24-48h of notification of the value
 
3. If confirmed, permanently discontinue study medication
 
4. Follow up until resolution or stabilization of laboratory abnormality(ies)

Serum creatinine increase 25 – 49% compared to baseline during normal hydration status	
Confirm 25% increase after 24-48h of notification of the value
 
Follow up within 2-5 days

Serum creatinine increase $\geq 50\%$ compared to baseline	
Confirm $\geq 50\%$ within 24-48 hours after receipt of the abnormal value
 
If confirmation of abnormal value is not possible in this timeframe study drug must be withheld until further evaluation is possible
 
Consider drug interruption
 
Consider patient hospitalization / specialized treatment

Albumin- or Protein-creatinine ratio increase ≥ 2 -fold compared to baseline	Confirm value after 24-48h of notification of the value
Albumin-creatinine ratio (ACR) ≥ 30 mg/g or ≥ 3 mg/mmol;	Perform urine microscopy
New dipstick proteinuria $\geq 1+$	Consider drug interruption / discontinuation
Protein-creatinine ratio (PCR) $>$ ULN	
New dipstick glucosuria $\geq 1+$ not due to diabetes	
Blood glucose (fasting)
 
Perform serum creatinine, ACR

New dipstick hematuria not due to trauma	
Urine sediment microscopy
 
Perform serum creatinine, ACR

Document contributing factors: co-medication, other co-morbid conditions, and additional diagnostic procedures performed in the CRF	
Monitor patient regularly (frequency at investigator's discretion) until one of the following: Event resolution: (sCr within 10% of baseline or protein-creatinine ratio within 50% of baseline) Event stabilization: sCr level with $\pm 10\%$ variability over last 6 months or protein-creatinine ratio stabilization at a new level with $\pm 50\%$ variability over last 6 months.	

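### Exclusion 14 bars raised creatinine only alongside renal disease, so a patient could enter already at the 1.5 mg/dL limb of Table 15-2, where it is unclear whether the permanent stop applies

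*Protocol*

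**What the plan says.** Protocol section 4.2, exclusion 14, reads "Acute or chronic renal disease with a screening serum creatinine > ULN". The closing sentence of the same section states: "No additional exclusions may be applied by the investigator". Exclusion 13 also calls for judgement: "Significant illness which has not resolved within two (2) weeks prior to initial dosing". Exclusion 4 includes a MELD cap of 15. No other inclusion or exclusion criterion visible in the copy reviewed sets a creatinine limit; exclusion 7 does not appear there.

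In Appendix 1, the first row of Table 15-2 is triggered by creatinine at least twice baseline or by an absolute value; the criterion ends "BL or ≥ 1.5 mg/dL". Its actions, in order, are to hold study drug; "Confirm increase after 24-48h of notification of the value"; "If confirmed, permanently discontinue study medication"; and then to follow up. Section 7.1 makes stopping mandatory for "A Liver or Renal event indicating discontinuation as defined in" Tables 15-1 and 15-2.

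In Part 1, eligibility is rechecked at baseline and baseline safety results are reviewed before the first dose (sections 3.1 and 4). In Part 2, randomisation follows the screening assessments (section 6.1.1), which fall between Day -84 and Day -14 (Table 8-2).

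**The concern.** An entry limit and a stopping limit for the same laboratory value should fit together: a patient admitted under the first should not already be at the second. Here they can fail to fit, because the entry limit depends on a diagnosis and the stopping limit does not. A patient could be randomised and dosed, then held for a value known before randomisation. What follows the hold depends on how the site reads one word in step 2. Two sites could treat the same stable value differently, one stopping treatment permanently and one not. At stake is consistent handling of individual patients.

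**Working it through.** The plan gives no figure to reproduce. The check is mainly one of logic, with a little arithmetic.

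**Can such a patient enter?**

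1. Exclusion 14 applies only if renal disease and creatinine above ULN are both present.
2. Take a screening creatinine of 1.5 mg/dL or more in a patient whom the investigator does not judge to have renal disease. The first condition fails, so exclusion 14 does not apply, whatever the laboratory's ULN.
3. No other visible criterion limits creatinine itself. Exclusion 13 needs a judgement of significant illness, and the MELD cap is a composite that may remove some patients.
4. The investigator may not add an exclusion. The Part 1 baseline review has no stand-alone creatinine limit to apply.

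**Is the patient at the trigger on entry?** Yes. The absolute limb makes no reference to baseline. Table 15-1 is different: its ALP and bilirubin rows use a multiple of baseline where the value was raised before treatment.

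**What must the site do?** The hold and the repeat test are clear. Suppose the repeat equals the entry value.

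- If confirmation means that the value is still at or above 1.5 mg/dL, step 3 requires a permanent stop.
- If confirmation means that an increase has been shown, nothing has increased and step 3 does not follow.

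The current wording supports either reading.

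**Distance from entry to the limb.** The formula is 1.5 / entry − 1. The entry values are assumed for illustration; the documents give no creatinine distribution.

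| Entry (mg/dL) | Calculation | Change at which the value equals 1.5 |
|---|---|---|
| 0.8 | 1.5/0.8 − 1 | +87.5% |
| 1.5 | 1.5/1.5 − 1 | 0% |
| 1.6 | 1.5/1.6 − 1 | −6.25% |
| 1.8 | 1.5/1.8 − 1 | −16.7% |

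For an entry value of 0.8 the limb marks a large rise. For entry values of 1.5 and above it is met with no rise, and can still be met after a fall.

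**Timing of the hold in Part 2.** The Day 1 chemistry result could prompt it when reported, so after about 0 days. Otherwise the next scheduled chemistry is Day 15, and 15 − 1 = 14 days. Of 12 × 7 = 84 planned treatment days, that is at most 14/84 = 17%.

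**The case against.** The best case for the plan has four parts.

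*The list is incomplete in the copy reviewed.* Exclusion 7 is not visible and cannot be assumed absent or irrelevant. This stands, and the point is therefore limited to the visible criteria.

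*The case is narrow.* Exclusion 14 does not require a previous diagnosis. Many investigators would call a creatinine of 1.5 mg/dL or more renal disease, or an unresolved significant illness. Tying an exclusion to a disease plus a value is also a legitimate choice. This stands too: it limits the size of the point but does not make the two limits fit together.

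*The table does not contradict itself.* A reader might infer a stronger fault from the footer, "Event resolution: (sCr within 10% of baseline or protein-creatinine ratio within 50% of baseline": a stable value would be at the stopping limb and resolved at the same time, so the table would license restarting drug. The documents do not support that. The footer says when monitoring ends and belongs with the follow-up in step 4. Step 3 governs stopping. A patient can be stopped permanently and later reach the end of monitoring without contradiction. The doubt rests only on the word for increase in step 2.

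*Harm is not shown.* On the stricter reading the patient stops. On the looser one the patient continues under scheduled chemistry, the relative creatinine rows of Table 15-2, and the investigator's duty under section 7.1 to stop where continuing would harm the patient. This stands: no route to unmonitored harm is identified, and the point is one of consistency.

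**Conclusion.** A minor mismatch, held with medium confidence. The visible criteria can admit a patient already at the 1.5 mg/dL limb, and for an unchanged entry value the text does not settle whether the permanent stop applies.

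This rests on three assumptions: that exclusion 7 sets no creatinine limit, that the investigator finds no renal disease or other excluding condition, and that exclusion 14 is read literally. The documents give no frequency; the number affected is very small and possibly zero.

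Two further inferences are not supported. One is that the trial would lose enough patients to affect power or the primary GGT result; nothing in the documents suggests it. The other is that the Amendment 6 summary, which describes the exclusion by creatinine alone, proves an error. A summary of changes is not operative text, and its difference from the current wording is not a fault in itself.

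**What to change.** Reword exclusion 14 to: *Screening serum creatinine > ULN (or ≥ 1.5 mg/dL, if lower)*, regardless of a renal diagnosis. The bracket is meant as whichever limit is stricter, so the edit works whatever the laboratory ULN is; the documents do not state it.

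Optionally, change step 2 of the first row of Table 15-2 to *Confirm value*, the verb that table already uses for the urinary ratios. The exclusion edit does not cover a Part 2 value that first reaches 1.5 mg/dL between screening and Day 1. With this second change, such a value, or any unchanged one, would be handled the same way at every site.

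The cost is one phrase, or two, in the protocol. Creatinine is already in the screening chemistry panel (section 8.4.4 and Table 8-2). The downside is a few more screen failures, including patients between ULN and 1.5 mg/dL who have no renal disease and are eligible now.
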